# 5.7. Treatment Compliance

Patients will be instructed to return treatment bottles at each visit. Compliance with dabrafenib and trametinib will be assessed through querying the patient during the site visits and documented in the source documents and eCRF.

A record of the number of dabrafenib and trametinib tablets dispensed to and taken by each patient must be maintained and reconciled with study treatment and compliance records. Treatment start and stop dates, including dates for treatment delays and/or dose reductions will also be recorded in the CRF. The investigator will make every effort to bring non-compliant patients into compliance.

## 5.8. Dose Modification Guidelines

The severity of AEs will be graded using the CTCAE, version 4.0. The section includes:

- general guidelines for clinically significant toxicities related to study treatments and
- specific guidelines for adverse events of special interest, which are events that have been observed with higher frequency or severity in patients receiving dabrafenib, trametinib, or a combination of both therapies.

**Note:** With the exception of pyrexia (likely related to dabrafenib), the guidance suggests that both therapies be reduced simultaneously in response to toxicities that are considered by the investigator to be treatment related.

Table 3 Categories of Dose Modification Guidelines

Adverse Event	Dabrafenib	Trametinib	Section
General Guidelines for Clinically Significant Toxicities	Х	Х	Section 5.8.2
Guidelines for Specific Adverse Event	s		
Cardiovascular Adverse Events			
LVEF	Х	Х	Section 5.8.3.1
Hypertension	Х	Х	Section 5.8.3.2
Prolonged QTc	Х	Х	Section 5.8.3.3
Skin –Related Adverse Events (Exce	pt cuSCC) a		
Rash	Х	Х	Section 5.8.4.1
Hand-Foot Skin Reaction	Х	Х	Section 5.8.4.2
Other Adverse Events			
Pyrexia	Х		Section 5.8.5.1
Diarrhea	Х	Х	Section 5.8.5.2
Renal Insufficiency	Х	Х	Section 5.8.5.3
Visual Changes	Х	Х	Section 5.8.5.4
Pneumonitis	Х	Х	Section 5.8.5.5
Liver Chemistry Stopping Criteria	Х	Х	Section 5.9

e. aRefer to Section 5.8.4.3 for management of cuSCC

#### 5.8.1. Dose Levels of dabrafenib and trametinib

The dose levels for this study are provided in Table 4.

Table 4 Dose Level Reduction Guidelines

Dose Level	Dabrafenib Dose/Schedule	Trametinib Dose/Schedule	
Starting Dose	150 mg BID	2 mg once daily	
-1 (1st Dose reduction)	100 mg BID	1.5 mg once daily	
-2 (2 nd Dose reduction)	75 mg BID	1.0 mg once daily	

Abbreviation: BID = twice daily

If an AE resolves to grade 1 or baseline at the reduced dose level, and no additional toxicities are seen after 4 weeks of study treatment at the reduced dose, the dose may be increased to the previous dose level.

A dose reduction below 75 mg BID for dabrafenib and 1 mg once daily for trametinib is not allowed. If a dose reduction below 75 mg BID for dabrafenib is required, dabrafenib will be permanently discontinued, but the patient will be allowed to continue trametinib. If a dose reduction below 1.0 mg once daily for trametinib is required, then trametinib will be permanently discontinued, but these patients will be allowed to continue dabrafenib.

Note: Approval from the GSK Medical Monitor is required to restart study treatment after  $\geq$ 21 days of interruption.

# 5.8.2. General Guidelines for Clinically Significant Toxicities

General guidelines regarding management and dose reduction for adverse events that are considered by the investigator to be related to study treatment and which do not have specific guidelines (Table 3) are provided in Table 5.

Table 5 Dose Modification Guidelines for Events Considered Related to Study Treatment

CTCAE Grade	Action and Dose Modification		
Grade 1	Continue study treatment at current dose level		
	Monitor closely		
	Provide supportive care according to institutional standards		
Grade 2	Interrupt study treatment if clinically indicated		
	Monitor closely		
	Provide supportive care according to institutional standards		
	When toxicity resolves to grade 1 or baseline, restart study treatment at current dose level		
Grade 3	Interrupt study treatment if clinically indicated		
	Monitor closely		
	Provide supportive care according to institutional standards		
	When toxicity resolves to grade 1 or baseline, restart study treatment reduced by one dose level		
	If the grade 3 toxicity recurs, interrupt study treatment		
	When toxicity resolves to grade 1 or baseline, restart study treatment reduced by another dose level		
Grade 4	Interrupt study treatment		
	Monitor closely		
	Provide supportive care according to institutional standards		
	Restart with study treatment reduced by one dose level once toxicity resolves to grade 1 or baseline		
	If the grade 4 toxicity recurs, either permanently discontinue study treatment or , if the patient is clinically benefiting, discuss continuation of study treatment with the GSK medical monitor.		

#### 5.8.3. Guidelines for Cardiovascular Adverse Events

Cardiovascular adverse events have been seen in patients receiving either dabrafenib, trametinib or both in combination. (See the IBs for additional information.)

## 5.8.3.1. Left Ventricular Ejection Fraction (LVEF)

Decreases of the left-ventricular-ejection-fraction (LVEF) have been observed in patients receiving trametinib monotherapy and in combination with dabrafenib. Therefore, ECHOs must be performed to assess cardiac ejection fraction at regular intervals as outlined in the Time and Events Table (Table 19). If possible ECHO assessment should be performed by the same operator throughout the study. Dose modification guidance and stopping criteria for LVEF decrease are provided in Table 6.

Table 6 Dose Modification Guidelines and Stopping Criteria for LVEF Decrease

Clinic	LVEF-drop (%) or CTCAE grade	Action and Dose Modification
Asymptomatic	Absolute decrease of >10% in LVEF compared to baseline and ejection fraction below the institution's LLN	Interrupt study treatment and repeat ECHO within 2 weeks a
		If the LVEF recovers within 4 weeks (defined as LVEF ≥LLN and absolute decrease ≤10% compared to baseline)
		Consult with the GSK medical monitor and request approval for restart
		Restart with trametinib or placebo reduced by one dose level
		Restart dabrafenib at previous dose level
		Repeat ECHO 2 , 4 , 8 and 12 weeks after re-start; continue in intervals of 12 weeks thereafter
		If LVEF does not recover within 4 weeks
		Consult with cardiologist
		Permanently discontinue study treatment
		Repeat ECHO after 2, 4, 8, 12, and 16 weeks or until resolution
		Consult with GSK medical monitor
Symptomaticb	Grade 3: resting LVEF 39-20% or >20% absolute reduction from baseline  Grade 4: resting LVEF <20%	Permanently discontinue study treatment.
		Consult with cardiologist
		Repeat ECHO after 2, 4, 8, 12, and 16 weeks or until resolution

Abbreviations: CTCAE = Common Terminology Criteria for Adverse Events; ECHO = echocardiogram; GSK = GlaxoSmithKline; LLN = lower limit of normal; LVEF = left ventricular ejection fraction;

a. If ECHO does not show LVEF recovery after 2 weeks, repeat ECHO 2 weeks later.

b. Symptoms may include: dyspnea, orthopenea, and other signs and symptoms of pulmonary congestion and oedema.

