- c. Symptomatic hypertension defined as hypertension aggravated by symptoms (e.g., headache, light-headedness, vertigo, tinnitus, episodes of fainting) that resolve after the blood pressure is controlled within the normal range.
- d. Persistent hypertension is defined as asymptomatic hypertension after initially successful anti-hypertensive intervention.

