- 11. Adverse events will be recorded from the time the first dose of study treatment is administered until 30 days after discontinuation of study treatment. Serious adverse events will be collected over the same time period as AEs except SAEs assessed as related to study participation (e.g., protocol-mandated procedures, invasive tests, or change in existing therapy), study treatment, or a GSK concomitant medication which must be recorded from the time a patient consents to participate in the study up to and including any follow-up contact.
- 12. At each timepoint listed, a single 12-lead ECG will be performed by qualified site personnel after the patient has rested in a semi-recumbent or supine position for at least 5 minutes.
- 13. While on treatment, patients who have an asymptomatic, absolute decrease in LVEF of > 10% compared to screening and whose ejection fraction is below the institution's LLN, must be followed according to LVEF guidelines for study drug management and requirements for subsequent ECHO.
- 14. All medications the patient takes during the study from the time of screening until 30 days after the last dose of study treatment will be recorded.
- 15. Analysis of clinical chemistry and haematology samples will be performed by the local lab. Screening labs performed within 2 weeks prior to randomisation do not need to be repeated.
- 16. Serum pregnancy test is required at Screening. Subsequent tests may be urine tests, and should be performed as clinically indicated.
- 17. A 4-week supply of study medication should be dispensed at each scheduled study visit as of Day 1. Patients should be provided with dosing instructions. Patients should start treatment as soon as possible after randomisation but no later than 72 hours post-randomisation.
- 18. Patients should be instructed to return study drug vials at each visit; compliance will be assessed through querying the patient and through pill count at the time of new dispensation. Dose modifications and interruptions must be recorded.
- 19. The date and exact time of PK sample collection and most recent dose will be recorded. Details of collection procedures, including dosing instructions for morning and afternoon visits, will be provided in the SPM.
- 20. End of study assessments do not need to be repeated if performed within 4 weeks
- 21. Biomarker-related sampling to be conducted at randomisation to avoid biomarker sample collection for ineligible patients

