#### 7.4.2.2. Definition of an SAE

A serious adverse event (SAE) is any untoward medical occurrence that, at any dose:

- a. Results in death;
- b. Is life-threatening;

**Note:** The term 'life-threatening' in the definition of 'serious' refers to an event in which the patient was at risk of death at the time of the event. It does not refer to an event, which hypothetically might have caused death, if it were more severe.

c. Requires hospitalization or prolongation of existing hospitalization;

**Note:** In general, hospitalisation signifies that the patient has been detained (i.e., usually involving at least one overnight stay) at the hospital or emergency ward for observation and/or treatment that would not have been appropriate in the physician's office or out-patient setting. Complications that occur during hospitalisation are AEs.

If a complication prolongs hospitalisation or fulfills any other serious criteria, the event is serious. When in doubt as to whether 'hospitalisation' occurred or was necessary, the AE should be considered serious.

BRF116613

Hospitalisation for elective treatment of a pre-existing condition that did not worsen from baseline is not considered an AE.

d. Results in disability/incapacity; and/or

**Note:** The term disability means a substantial disruption of a person's ability to conduct normal life functions. This definition is not intended to include experiences of relatively minor medical significance such as uncomplicated headache, nausea, vomiting, diarrhoea, influenza, and/or accidental trauma (e.g., sprained ankle) which may interfere or prevent everyday life functions but do not constitute a substantial disruption.

e. Is a congenital anomaly/birth defect. Medical or scientific judgment should be exercised in deciding whether reporting is appropriate in other situations, such as important medical events that may not be immediately life-threatening or result in death or hospitalisation but may jeopardize the patient or may require medical or surgical intervention to prevent one of the other outcomes listed in the above definition. These should also be considered serious. Examples of such events are invasive or malignant cancers, intensive treatment in an emergency room or at home for allergic bronchospasm, blood dyscrasias, or convulsions that do not result in hospitalisation, or development of drug dependency or drug abuse.

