# f. Protocol-specific SAEs:

• All events of possible drug-induced liver injury with hyperbilirubinemia defined as ALT ≥3 x ULN and total bilirubin ≥2 x ULN (>35% direct) or ALT ≥3 x ULN and INR >1.5 (if INR is measured) or termed 'Hy's Law' events (INR measurement is not required and the threshold value stated will not apply to patients receiving anticoagulants).

**Note**: Bilirubin fractionation is performed if testing is available. If testing is unavailable, record presence of detectable urinary bilirubin on dipstick indicating direct bilirubin elevations and suggesting liver injury. If testing is unavailable and a patient meets the criterion of total bilirubin  $\geq 2$  x ULN, then the event is still reported as an SAE. If INR is obtained, include values on the SAE form. International normalized ratio (INR) elevations  $\geq 1.5$  suggest severe liver injury.

- Any new malignancy with a histology different from the primary tumour, including cutaneous squamous cell carcinoma
- Laboratory abnormalities as referenced in Section 7.4.2.3.
- LVEF that meets stopping criteria Section 5.8.3.1
- CSR or RVO

 Pyrexia accompanied by ≥ Grade 3 hypotension or hypotension that is clinically significant in the judgement of the investigator, or dehydration requiring IV fluids, or severe rigors/chills.

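### Table 6 has no mandatory LVEF rule for a symptomatic patient with LVEF from 40% to below LLN and a fall of >10 to 20 points, although the same echocardiogram without symptoms forces interruption

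*Protocol*

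**What the plan says.** Table 6 in Protocol Section 5.8.3.1 has two rows.

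- **Asymptomatic.** The trigger is "Absolute decrease of >10% in LVEF compared to baseline" together with an ejection fraction below the institution's LLN. The action is "Interrupt study treatment and repeat ECHO within 2 weeks". If LVEF recovers within 4 weeks, restart needs the medical monitor's approval, trametinib is reduced by one dose level, and further ECHOs follow. If it does not recover, treatment stops permanently and a cardiologist is consulted.
- **Symptomatic.** The trigger is "Grade 3: resting LVEF 39-20% or >20% absolute reduction from baseline", or Grade 4 (resting LVEF below 20%). The action is permanent discontinuation, cardiology consultation and repeat ECHOs.

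Three other places bear on the point.

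- Table 19 footnote 13 makes the LVEF guidelines binding, but for "patients who have an asymptomatic, absolute decrease in LVEF of > 10% compared to screening" and below LLN.
- The Table 19 ECHO row schedules on-treatment scans at Week 4 and then every 12 weeks, each ±7 days.
- Section 7.4.2.2 lists as a protocol-specific SAE "LVEF that meets stopping criteria Section 5.8.3.1".

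**The concern.** The two rows are divided by symptoms but use different LVEF thresholds, so together they do not cover every LVEF decrease that the first row treats as actionable. A patient who has symptoms and LVEF between the thresholds is excluded from the first row by the symptoms and from the second by the LVEF value.

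Applied literally, the sicker patient loses the mandatory interruption, the 2-week ECHO, the LVEF-specific restart approval and the 4-week recovery limit that the less sick patient receives. This runs against the protocol's own approach. At Grade 3 and 4, symptoms in Table 6 lead to the stricter outcome, and in Table 7, Scenario C, symptomatic hypertension is enough on its own to require interruption.

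The point matters here because decreased ejection fraction is a known trametinib effect (7% in the Phase 3 monotherapy trial, Section 1.1.2), all three arms are planned to receive trametinib, and there is no IDMC (Section 10.8). Patient-level rules therefore carry more of the safety protection.

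**Working it through.** **Inputs**

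- Asymptomatic trigger (Table 6): baseline − current > 10 points, and current < LLN.
- Symptomatic trigger (Table 6): current ≤ 39%, or baseline − current > 20 points. Grades 3 and 4 together cover every value of 39% or less.
- Baseline (Sections 4.1.2 and 4.1.3): at or above LLN, because LVEF below LLN is excluded.
- LLN: institutional, with no number in the documents. Values of 45%, 50%, 55% and 60% are assumed.
- LVEF is taken in whole percentage points, with baselines up to 80%.

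**The gap.** A symptomatic patient is uncovered when the first trigger is met and the second is not:

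- fall from 11 to 20 points, and
- LVEF from 40% to LLN − 1.

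A fall of exactly 20 points is inside the gap, because the symptomatic criterion is strictly greater than 20.

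**One patient, LLN 50%.** Baseline 60%, now 45%. The fall is 60 − 45 = 15.

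- Asymptomatic rule: 15 > 10 and 45 < 50, so it is met.
- Symptomatic rule: 45 > 39 and 15 ≤ 20, so it is not met.

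**Extent.** For baseline b, the uncovered LVEF values run from max(40, b − 20) to min(LLN − 1, b − 11).

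| Assumed LLN | Uncovered (baseline, current) pairs | Uncovered LVEF range |
|---|---|---|
| 45% | 50 | 40–44% |
| 50% | 100 | 40–49% |
| 55% | 140 | 40–54% |
| 60% | 155 | 40–59% |

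- LLN 50%: the gap exists for baselines 51–69%. Baseline 55% gives 40–44, baseline 60% gives 40–49 (the widest, 10 values), and baseline 65% gives 45–49.
- LLN 55%: the gap exists for baselines 55–74%. Baseline 60% gives 40–49, 65% gives 45–54, and 70% gives 50–54.

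The gap exists for any LLN above 40%.

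**Time to the next mandated ECHO.** Without symptoms it is at most 2 weeks. In the gap it is the next scheduled scan: Week 12 − Week 4 = 8 weeks, then Week 24 − Week 12 = 12 weeks, each visit ±7 days. These intervals apply when the abnormal ECHO was itself a scheduled one. If it was unscheduled, the wait can be shorter.

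**Does other text fill the gap?**

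- Table 19 footnote 13: no. It carries the same asymptomatic restriction.
- Table 5 (Section 5.8.2): it covers related events that have no specific guideline, and Table 3 lists LVEF as having one. A related symptom such as dyspnoea could be handled there as a separate event, but at Grades 2 and 3 the instruction is "Interrupt study treatment if clinically indicated", with no ECHO step.
- Section 4.2.1: an unacceptable adverse event ends combination treatment, and the investigator may stop treatment. Neither sets an LVEF threshold or an ECHO.
- Section 7.4.2.2: the protocol-specific bullet refers back to stopping criteria in 5.8.3.1, so it does not clearly include this patient. The general criterion for events that "may jeopardize the patient or may require medical or surgical intervention to prevent one of the other outcomes" can still apply.

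**The case against.** The strongest reply is that the practical risk is small. A clinician would naturally read the asymptomatic rule as a minimum and would hardly continue treatment in a breathless patient whose ejection fraction has fallen 15 points.

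There is also more cover than Table 6 alone suggests. At Grades 2 and 3, Table 5 asks without condition for close monitoring and supportive care. At Grade 3 it adds a dose reduction on restart and unconditional interruption on recurrence, and at Grade 4 it requires interruption outright. Section 5.8.1 requires the medical monitor's approval to restart after any interruption of 21 days or more. An important medical event is an SAE, reportable within 24 hours. The 8- and 12-week figures are maximum waits. Few patients would be affected: 7% of 54 is 0.07 × 54 = 3.8, so about 4 patients with any ejection-fraction decrease if the monotherapy rate applied throughout, and the gap is a subset of those. The hypertension comparison involves a different toxicity and shows inconsistency rather than error. Section 5.8.3 also refers readers to the Investigator Brochures, which are not available here.

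Most of this is fair on likelihood, and it stands as a limit on how serious the point is. It does not close the gap. None of the cited text mandates interruption at Grade 2 or at a first Grade 3 event, and none mandates a repeat ECHO. The 21-day approval rule applies only once treatment has been interrupted for that long. A stopping rule is there so that the decision does not rest on judgement alone, and this one covers the milder presentation while omitting the more worrying one.

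**Conclusion.** The concern holds. For a symptomatic patient with LVEF from 40% to below LLN and a fall of >10 to 20 points, the protocol sets no mandatory LVEF-specific action, whereas the same LVEF without symptoms requires interruption and an ECHO within 2 weeks.

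The existence of the gap follows from the wording and needs only an LLN above 40%. Its width depends on the institutional LLN, which is assumed: at 50% or 55% it spans up to 10 whole-number LVEF values at a given baseline. The documents do not say how many symptomatic patients to expect in this range, or whether the omission was intended. The number is likely to be small.

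This is a patient-safety drafting gap with no bearing on the endpoints or their analysis. It should be corrected.

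**What to change.** 1. In Table 6, apply the interruption, 2-week ECHO, restart-approval and 4-week recovery rules to any absolute fall of more than 10 points with LVEF below LLN, with or without symptoms, as a minimum. Keep the symptomatic Grade 3/4 row as the stricter rule. Falls of 10 points or less stay outside, as now.
2. Have the safety team decide whether symptomatic patients in this range may restart after recovery or must stop permanently, and state the answer in the table.
3. Delete the word asymptomatic from Table 19 footnote 13.
4. State in Section 7.4.2.2 that the LVEF SAE trigger includes this case.

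The cost is one row label, one word and one SAE bullet in an amendment, plus the clinical decision in item 2. The downside is a few more treatment interruptions, in patients who have symptoms and a documented LVEF fall.

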#### 5.8.3.2. Hypertension

Increases in blood pressure have been observed in patients receiving trametinib. Recommendations for blood pressure monitoring and management are provided in this section.

## **Monitoring of Hypertension**

All blood pressure assessments should be performed under the following optimal conditions:

- the patient has been seated with back support, ensuring that legs are uncrossed and flat on the floor
- the patient is relaxed comfortably for at least 5 minutes
- restrictive clothing has been removed from the cuff area and the right cuff size has been selected
- the patients arm is supported so that the middle of the cuff is at heart level
- the patient remains quiet during the measurement.

In patients with an initial blood pressure reading within the hypertensive range, a second reading should be taken at least 1 minute later, with the 2 readings averaged to obtain a final blood pressure measurement. The averaged value should be recorded in the eCRF.

Persistent hypertension is defined as an increase of systolic blood pressure (SBP) > 140 mm Hg and/or diastolic blood pressure (DBP) > 90 mm Hg in three consecutive visits with blood pressure assessments from two readings collected as described above. Visits to monitor increased blood pressure can be scheduled independently from the perprotocol visits outlined in the Time and Events Table (Table 19). Ideally, subsequent blood pressure assessments should be performed within one week.

Asymptomatic hypertension is defined as an increase of SBP >140 mm Hg and/or DBP >90 mm Hg in the absence of headache, light-headedness, vertigo, tinnitus, episodes of fainting or other symptoms indicative of hypertension that resolve after the blood pressure is controlled within the normal range.

